1 - **HUMAN SUBJECTS RESEARCH PROTOCOL**

2 **COVER PAGE**

3

4

5

6

7

8 **Official Study Title:** Enhancing Prolonged Exposure with Cannabidiol to

9 Treat PTSD

10

11 **NCT number:** NCT05132699

12

13 **IRB Approval Date:** 11-15-2022

14

15

16 **Unique Protocol ID:** HSC20210711H

17

18

19

20

21

22

23

24

25

26

27

28

29

30

31

32

33

34

35

36

37

38

39

40

41

42

43

44 **1. PROTOCOL TITLE:** Enhancing Prolonged Exposure with Cannabidiol to Treat PTSD45 **2. ABSTRACT**

46 Posttraumatic stress disorder (PTSD) is considered a signature psychiatric disorder among military populations. When left
47 untreated, the symptoms of PTSD can cause significant health and functional impairments. While established treatments
48 for PTSD exist, there remains room for improvement in outcomes since almost half of military patients fail to benefit from
49 treatment. Epidiolex (Cannabidiol [CBD]) is an FDA-approved, non-controlled prescription medication with promising
50 potential for the treatment of PTSD.^{1,2} To date, there are no published clinical trials investigating CBD in reducing PTSD,
51 and existing literature in humans with PTSD only includes healthy individuals or case study data. Greater research is
52 needed to fully understand the benefits of CBD for PTSD and to better understand biological mechanisms for its effect.
53 The primary goal of this pilot project is to demonstrate the safety and feasibility of using CBD in combination with standard
54 of care prolonged exposure (PE) psychotherapy to reduce PTSD symptoms (Aim 1). We will also assess possible
55 biochemical and physiological outcomes associated with treatment (Aim 2) and evaluate the relationship between
56 changes in biochemical/physiological measures with PTSD symptom reductions (Aim 3). To address study aims, we will
57 enroll 24 individuals with PTSD to be randomized to CBD (n=12) or placebo (n=12) and all participants will receive 10
58 daily sessions of PE.

60 **3. OBJECTIVES/SPECIFIC AIMS/RESEARCH QUESTIONS**

61 This project will be a pilot, double-blind randomized controlled trial of CBD effects to pursue three goals: (1) to
62 demonstrate the safety and feasibility of using CBD to reduce PTSD symptoms in conjunction with massed PE (mPE); (2)
63 to assess biochemical and physiological outcomes associated with PTSD treatment; and (3) to evaluate the possible
64 relationship between changes in biochemical/physiological measures with PTSD symptom reductions.

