
65 **Aim 1:** To examine the safety, feasibility, and PTSD symptom reductions associated with CBD (n=12) vs. placebo (n=12)
66 in 24 individuals receiving 10 daily sessions of mPE as a standard of care for PTSD.

67 Hypothesis 1: Combining CBD with mPE will be safe based on minimal (< 5%) adverse events and no serious adverse
68 events related to treatment in the study.

69 Hypothesis 2: A CBD vs. placebo trial design will be feasible defined as 75% or more of assessed individuals meeting
70 all eligibility criteria and 80% or more of CBD participants completing all 10 mPE sessions.

71 Hypothesis 3: Participants in the CBD condition will have greater treatment-related PTSD reductions than placebo as
72 measured by the Clinician Administered PTSD Scale (CAPS-5)³ and PTSD Checklist (PCL-5).⁴

73 **Aim 2:** To evaluate biochemical and physiological levels associated with the eCB system and stress response in CBD vs.
74 placebo.

75 Hypothesis 4: Participants in the CBD condition will have higher levels of AEA and 2-AG, and lower levels of cortisol
76 than placebo following treatment.

77 Hypothesis 5: Participants in the CBD condition will have lower average heart rate during exposure therapy sessions
78 than placebo.

79 **Aim 3:** To determine the association between changes in biomarker levels (cortisol, AEA, 2-AG), physiology (heart rate),
80 and PTSD symptom reduction following treatment.

81 Hypothesis 6: Reductions in cortisol and increases in AEA and 2-AG will be associated with PTSD symptom reductions
82 following treatment.

83 Hypothesis 7: Lower average heart rate observed during exposure therapy sessions will be associated with PTSD
84 symptom reductions following treatment.

85 **4. MILITARY RELEVANCE**

86 As compared to civilians, the rate of PTSD is particularly elevated among military populations, with approximately 23% of
87 military vs. 6-8% of civilians meeting criteria for PTSD.⁵ PTSD has been identified as the signature deployment-related
88 psychiatric condition among service members. The functional impact of PTSD can cost service members their military
89 careers and veterans with PTSD are at increased risk of unemployment and homelessness following military separation.⁶
90 Notwithstanding evidence that PE is an effective treatment for PTSD, there remains room for improvement in outcomes
91 given that a large proportion of patients (~50%) fail to significantly benefit from treatment.⁷ This issue is especially

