199 PTSD symptom change associated with CBD 250mg taken twice a day for 18days (n=12) vs. placebo (n=12) in
200 combination with a standard of care, 10-sessions mPE psychotherapy administered over 2 weeks. Aims 2 and 3 will
201 evaluate biochemical and physiological outcomes associated with eCB and PTSD that may be affected by CBD.
202 Permuted block randomization is advantageous in small clinical trials to ensure equal allocation of participants in each
203 condition. Participant randomization will be subdivided into randomized blocks of four, two patients in each block will be
204 assigned to CBD and two will be assigned to placebo. Randomization will occur after the participant consents to the study
205 and eligibility is determined. [name] (Co-Mentor on this KL2) will determine randomization codes and
206 coordinate with the compounding pharmacy (Oakdell Pharmacy) providing the medication and placebo for this trial to
21-711H, [name], Form BB, 11-15-22, AMD.docx

207 ensure blocking procedures are appropriately carried out. All other study team members will be blinded to randomization.
 208 The study assessments and the timing for repeated assessments conducted are described in detail in section 7.3.

Figure 1. General Study Design Overview

Notes. See Section 7.3 for detailed study procedures.

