7. RESEARCH PLAN

7.1 Selection of Subjects

Number of subjects to be screened for eligibility: 40

Target number randomized: 28

Target enrollment number for completers: 24

7.1.1. Subject Population.

Individuals between 18-65 years old recruited from the San Antonio community will be invited to participate in this research.

Efforts will be tailored to equally recruit diverse individuals across sex, gender/sexual orientation, race, age, disability, socioeconomic status, national origin, and branch of military service.

7.1.2. Inclusion and Exclusion Criteria.

Inclusion Criteria

1. Individuals between the age of 18 to 65 years old at time of screening.
2. Able to write, read, and speak English
3. PTSD diagnosis as assessed by Clinician-Administered Posttraumatic Stress Scale (CAPS-5)
4. Stable medication regimen for at least four weeks prior to the onset of study participation.

Exclusion Criteria

1. History of opiate, cocaine, methamphetamine, benzodiazepine, or cannabis abuse as determined by the National Institute of Drug Abuse Quick Screen (NIDA-Q).
2. Currently using opiates, cocaine, methamphetamines, benzodiazepines, or cannabis as evidenced by a positive urine drug screen prior to enrollment.
3. Currently pregnant as determined by a positive urine pregnancy test prior to enrollment.
4. Current clinically significant alcohol abuse in the past two weeks on the Quick Drinking Screen (QDS).
5. Currently breastfeeding.

238 6. Ongoing illness or physical health problem(s) that may be exacerbated by CBD (e.g., history of liver problems)
239 7. History of significant allergic condition, significant drug-related hypersensitivity, or allergic reaction to
240 cannabinoids.
241 8. Regular use of the following concomitant medications because of the possible interaction with CBD
242 • The anti-convulsant/anti-epileptics Carbamazepine and Phenytoin
243 • The atypical antipsychotics Olanzapine, Quetiapine, and Risperidone
244 • The entire class of barbiturates (Sedative-Hypnotics)
245 • Chronic, daily use of any class of benzodiazepines. Intermittent or as needed dose of a benzodiazepine will
246 be allowed.
247 • The miscellaneous hypnotics Zaleplon, Zolpidem, Eszopiclone, Ramelteon, and Suvorexant
248 • The herbal supplement St. John's Wort.
249 • The entire class of glucocorticoids
250 • Use of platelet inhibitors Clopidogrel and Warfarin unless the participant is on a stable dose.
251 • The antiretrovirals Ritonavir and Indinavir

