- 322 • Location where study product(s) will be stored: The medication will be received from Oakdell Pharmacy by a 323 trained study team member and transported to the STRONG STAR clinic where it will be stored in a locked 324 cabinet until the participant arrives to receive the medication at the medication review appointment.
- 325 • Dose range, schedule, and administration route of study product(s): 2.5 mL (250mg) taken twice daily in the 326 morning and evening after meals for (500mg per day) for 18 consecutive days beginning three days prior to the

327 start of mPE. Epidiolex and placebo will be prepared by Oakdell Pharmacy in a strawberry-flavored liquid solution
 328 administered using an oral syringe.

329 • Plan for disposition of unused study product(s): Any unused study products will be disposed of in accordance with
 330 the STRONG STAR Drug Accountability and Storage SOP.
 331 • FDA status: The FDA has approved the use of Epidiolex for seizure disorders. Prior research has demonstrated
 332 the safety and early positive benefits of off-label use of Epidiolex for Anxiety and Trauma-Related symptoms in
 333 humans. We are not seeking a new indication with this research project.

334 7.3. Research Interventions/Study Procedures.

335 **Interventions.**

336 Participants will be randomized to either Epidiolex (CBD) or placebo. All participants will receive 10 sessions of mPE
 337 administered weekdays over 2 weeks.

338 Epidiolex (CBD) is an FDA approved, non-controlled prescription medication indicated for the treatment of seizure
 339 disorders. Prior research has demonstrated the safety and early positive benefits of off-label use of CBD for Anxiety and
 340 Trauma-Related symptoms in humans. CBD comes in a 100-mL bottle containing 100 mg of CBD per ml of strawberry-
 341 flavored liquid solution that is taken using an oral syringe. Strawberry-flavored liquid solution is also available for Oakdell
 342 pharmacy to create a comparable placebo to maintain the blind. Starting recommended dose is 2.5 mL (250mg) taken
 343 twice daily (total = 5 mL/500mg) in the morning and evening after meals.¹ We will employ this dosing recommendation for
 344 this study for 18 consecutive days. Steady state has been shown to occur in 2 days.⁴¹ To ensure maintenance on an
 345 adequate steady state dose for all randomized participants, we will begin medication 3 days prior to the start of mPE. CBD

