All biospecimen samples will be transported to the BPAL in the UTHSA Department of Psychiatry and Behavioral Sciences at the UT Health-Long School of Medicine in room 727F for processing and storage. This location is monitored 24-7 by a wireless monitoring system on the Isensix system.

401 402 7.3.1.1 Laboratory evaluations and special precautions:

403 All biospecimen collection procedures will be carried out by trained team members and appropriately transported, stored,
404 and disposed of in accordance with STRONG STAR Biomarkers and Genomics Services SOP, International Air Transport
405 Association (IATA), and UTHSA IRB guidelines. All samples will be labeled with coded subject numbers and dates to
406 protect the identities of participants.

407 At the times designated in Section 7.3 Table, 7mL of venous blood will be drawn into one purple top tube for
408 measurement of AEA, 2-AG, and CBD levels. Immediately upon collection, blood will be labeled, mixed, and chilled on
409 ice. This blood will be transported to the BPAL as soon as possible, where it will be processed to separate out the plasma.
410 Plasma will be aliquotted into two cryovials, labeled, and placed in the STRONG STAR-CAP biorepository for long-term
411 storage at -80° C. Samples will be later analyzed in batches using HPLC/Tandem Mass Spectrometry.

412 On the days designated in Section 7.3 Table, saliva samples will be collected by participants immediately upon awakening
413 in the morning. Samples are collected by passive drool saliva collection into saliva sample tubes labeled only by coded
414 subject number and Day number. Participants will be instructed to refrigerate the sample upon collection and to bring the
415 salivette to their next scheduled appointment. Saliva samples will be collected from the participant by study staff when the
416 participant arrives for their appointment and immediately chilled in a cooler filled with ice and then brought to the BPAL for
417 storage at -20° C as soon as possible. Subjects will bring these samples to their visit appointment and staff will receive
418 them and transport them to the BPAL for long-term storage until later analysis for cortisol levels.

419 420 7.3.2 Data Collection.

421 See Table in Section 7.3 for a summary of the assessments and timing of administration. The data collected in the study
422 will be coded using an assigned number. Hard copies of data collected during the study will be securely stored in locked

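### In Hypothesis 2, mPE session completion is the only treatment-delivery measure: neither leg captures whether study drug was taken, and the planned plasma CBD result has no stated use

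*Combined protocol and SAP*

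**What the plan says.** The first goal in section 3 is to show that CBD can be used safely and feasibly alongside massed PE. The definition reads: "Hypothesis 2: A CBD vs. placebo trial design will be feasible defined as 75% or more of assessed individuals meeting" "all eligibility criteria and 80% or more of CBD participants completing all 10 mPE sessions". It has two legs, eligibility and session completion in the CBD arm.

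Sections 7.2.1 and 7.3 describe 2.5 mL taken twice daily for 18 days, starting three days before therapy so that participants are at steady state. The bottle is handed over at the medication review visit. The only text on accountability concerns disposal of unused product under "the STRONG STAR Drug Accountability and Storage SOP".

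Section 7.3.1 schedules four blood draws: before the medication review and before PE sessions 1, 5 and 10. Section 7.3.1.1 says the blood is for "measurement of AEA, 2-AG, and CBD levels". The assessment table lists only AEA and 2-AG for that draw. Section 7.4.2 names CAPS-5, PCL-5 and adverse events as primary and does not mention plasma CBD. Section 7.4.3 handles feasibility by descriptive statistics and analyses outcomes by intention to treat; it does not mention plasma CBD either.

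**The concern.** The pilot is meant to prepare for a larger trial of CBD added to mPE. What is new in that combination is the drug, yet the criterion for treatment delivery is attendance at therapy. A participant who stops the solution after a few days but attends all ten sessions counts as a success.

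Two things are at stake. First, the design could be reported as feasible when the drug was largely not taken. Second, if the arms do not differ on PTSD symptoms, AEA or 2-AG, the reader will ask whether the CBD arm was exposed and the placebo arm was not. The plan collects data that bear on this but does not commit to showing them.

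**Working it through.** **1. The plan's own figures.** Section 7.4.1 gives 24 completers + 4 dropouts = 28 randomised, and 28 + 12 screen failures = 40 consented. The 30% screen failure is 12/40. The printed 17% dropout is 4/24 = 16.7%; as a share of those randomised it is 4/28 = 14.3%. These totals reproduce. The 75% and 80% thresholds have no stated derivation, so there is nothing to reproduce for them.

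**2. What each leg depends on.**
- Eligibility leg: fixed at screening, before the first dose.
- Session leg: a count of therapy sessions.
- Scheduled drug-taking: 18 days × 2 = 36 doses, or 36 × 2.5 mL = 90 mL per participant. No diary, returned-volume measure, adherence definition or adherence threshold is described.

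**3. The count needed.** With 12 in the CBD arm, 80% requires 10 (10/12 = 83.3%; 9/12 = 75% fails). If 28 are randomised 1:1, the arm is 14 and 12 are needed (12/14 = 85.7%; 11/14 = 78.6% fails).

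**4. Probability that the session leg is met.** P = Σ C(n,k) p^k (1−p)^(n−k), summed from the required count to n. I assume p = 24/28 = 0.857, taking the plan's completers as people who finish all ten sessions; the protocol does not say this. For n = 12:
- k = 10: 0.288
- k = 11: 0.315
- k = 12: 0.157
- Sum: 0.76

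At p = 0.80 and 0.90 the sum is 0.56 and 0.89. For n = 14 and p = 0.857 it is 0.68. Adherence does not appear in the formula.

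**5. Illustration of a rule that does respond.** Suppose a success required all ten sessions and adherence to study drug, still at 80% of the arm. Assume adherence is independent of attendance, so p becomes 0.857 × a.

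| Adherence a (assumed) | Session leg, n=12 | Joint rule, n=12 | Session leg, n=14 | Joint rule, n=14 |
|---|---|---|---|---|
| 100% | 0.76 | 0.76 | 0.68 | 0.68 |
| 90% | 0.76 | 0.46 | 0.68 | 0.35 |
| 80% | 0.76 | 0.22 | 0.68 | 0.13 |
| 70% | 0.76 | 0.08 | 0.68 | 0.04 |
| 50% | 0.76 | 0.005 | 0.68 | 0.001 |
| 0% | 0.76 | 0 | 0.68 | 0 |

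The table shows the insensitivity of the present leg. It does not recommend this particular joint rule.

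**6. Where plasma CBD appears.** It is named once, among the laboratory measurements. It is absent from the assessment table, the endpoints and the analysis section. Three of the four samples follow the start of dosing (study days 4, 8 and 15).

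**The case against.** Several points on the other side are sound.

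- **Sessions are not the whole criterion.** A reader might infer that feasibility rests on attendance alone. It does not: the eligibility leg must also be met, and the plan's own figures make that uncertain. From "Number of subjects to be screened for eligibility: 40" and 28 randomised, the expected eligible share is 28/40 = 70%, below 75%. At a true 70%, P(at least 30 of 40) = 0.31. If the legs are treated as independent and the arm stays at 12, both are met with probability of about 0.309 × 0.760 = 0.23. A wrong declaration of feasibility is thus less likely than the session leg alone suggests. The eligibility leg still carries no information about drug-taking.
- **Exposure is measured.** A reader might infer that adherence in the CBD arm and stray CBD use in the placebo arm go unassessed, so that a null could never be interpreted. Section 7.3.1.1 rules this out: CBD is assayed, with no restriction by arm, so exposure around three visits can be examined. What is missing is a commitment to report it.
- **The SOP is not in the documents.** It may already require bottles to be returned and measured. Even so, no adherence result reaches Hypothesis 2 or section 7.4.
- **Hypothesis 2 is descriptive.** Nothing makes it a binding go/no-go rule, and nothing prevents adherence from being reported beside it. An intention-to-treat effect that includes non-adherence is also a legitimate planning input. This lowers the stakes, but the protocol still attaches the word feasible to this definition.
- **Three samples cannot show adherence over 18 days.** Someone dosing only around visits could test positive. This stands, and it is why a volume measure is also needed.

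**Conclusion.** The point holds in this form: session completion is the only treatment-delivery measure in Hypothesis 2, neither leg captures drug-taking, and plasma CBD has no planned use. The structural finding needs no assumption. The probability of 0.76 (0.68 with 14 in the arm) rests on an assumed completion rate of 24/28; its independence of adherence does not.

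It is tempting to go further and state how much a treatment effect would be diluted by non-adherence. The documents give neither an effect size nor a non-taking rate, so any such figure would be invented. With 12 per arm the standard error of a standardised difference is about √(1/12 + 1/12) = 0.41, a 95% interval of roughly ±0.8, which would swamp modest dilution. The case rests on the feasibility definition and the missing exposure summary. It is worth correcting, and it does not invalidate the trial.

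**What to change.** 1. Add a pre-specified drug-taking component to Hypothesis 2 and report it for both arms. One option is volume used (dispensed minus returned) against the scheduled 90 mL. The sponsor should set the threshold and say whether it is a separate leg or combined with session completion.
2. List plasma CBD in the assessment table with AEA and 2-AG, and give it a stated use in section 7.4.
3. After unblinding, report the percentage of samples with measurable CBD by arm at sessions 1, 5 and 10. Place it beside the AEA, 2-AG and symptom contrasts, with a note that three samples show exposure around those visits and not adherence over all 18 days.

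The blood draws and assay are already planned, so the added work is one table and, unless the SOP already requires it, recording returned volume. The price is a feasibility criterion that is harder to meet, as the illustration shows. No dose or clinical rule changes.

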178 system since research has shown that CBD may have low affinity for CB receptors, but nonetheless is able to bind to
179 CB1.³⁹ CBD may also act as an antagonist to other agonists due to effects at different prejunctional sites and indirect
180 interactions with non-cannabinoid receptors.⁴⁰ In turn, this may explain possible effects on eCB metabolism including
181 inhibition of the uptake and degradation of critical eCBs associated with stress response including AEA and 2-AG.

[figure not shown]
182 **Innovation.** Additional research is warranted to fully understand the benefits of CBD for PTSD. Currently, there are no
183 published clinical trials investigating the efficacy of CBD in reducing PTSD and existing PTSD literature in humans only
184 includes healthy individuals or case study data. Research on cannabinoids and PTSD remains in the early stages of
185 development and more research is needed to understand how CBD modulates the eCB system. Based on existing
186 research, the next logical step is to investigate CBD as an augmentation treatment for an established psychotherapy that
187 targets extinction learning mechanisms for PTSD symptom reduction. This proposal will examine CBD as an adjunct for
188 mPE and explore potential biological mechanisms for its effect, making it the first study of its kind. Findings from this study
189 have the potential to improve outcomes among military and civilians with PTSD and mitigate the personal, social, and
190 economic costs of this debilitating, chronic condition. This study will also expand understanding of the relationship
191 between PTSD, CBD, and the eCB system.

192 6. RESEARCH DESIGN

193 This study is an early Phase II double-blind, pilot randomized controlled clinical trial. We will use a permuted block
194 randomization design stratified by PTSD severity median score of 51 on the PCL-5 and population type (military or
195 civilian). The median score stratification was derived from a recently completed STRONG STAR randomized clinical trial
196 of military veterans seeking treatment for PTSD (manuscript in press). The decision to stratify by population was based on
197 existing literature that has found differences in treatment response between military and civilian samples (e.g., Steenkamp
198 et al., 2015; [name] et al., 2019). Participants will be 24 individuals with PTSD to investigate the safety, feasibility, and

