 346 and matching placebo for this study will be obtained through Oakdell Pharmacy which will obtain a sufficient supply of
 347 CBD for 12 participants from their supplying manufacturer. They will then prepare CBD (n = 12) and matching placebo (n
 348 =12) dosage for 24 participants in blinded containers that will be numbered per the randomization design. The medication
 349 and placebo will be dispensed to a trained study team member and transported in a locked container to the STRONG
 350 STAR Clinic where it will be stored in a locked cabinet until the participant arrives to receive the medication at the
 351 medication review appointment 3 days prior to beginning mPE.

352 Massed Prolonged Exposure (mPE). Prolonged Exposure (PE) is a first-line, empirically supported cognitive behavioral
 353 treatment for PTSD and serves as the foundation for mPE.¹⁶ mPE, delivered daily Monday through Friday over two
 354 weeks, utilizes exposure-based interventions to target psychological mechanisms (i.e., experiential and behavioral
 355 avoidance; maladaptive cognitive changes) that are thought to maintain trauma-related symptoms. Ten 90-minute
 356 sessions of mPE, which has been found to be non-inferior to ten 90-minute spaced PE delivered once or twice a week
 357 over eight weeks, helps minimize military-specific treatment barriers, and decreases treatment dropout rates.¹⁴ For this
 358 study, each participant will receive ten 90-minute mPE daily over two weeks. Up to 19 days following initiation of the
 359 medication regimen will be allowed to complete the ten sessions of mPE to accommodate scheduling constraints.
 360 Consistent with the standard spaced PE therapy manual, mPE includes four primary treatment components: (1)
 361 psychoeducation on common reactions to trauma; (2) relaxation training; (3) in vivo exposure; and (4) imaginal exposures.
 362 In vivo exposure involves approaching avoided situations, people, places, and/or objects that are realistically safe. With
 363 imaginal exposure, participants repeatedly and systematically revisit their trauma memory and related thoughts and
 364 feelings. Participants also will be asked to complete homework, including reviewing treatment materials, listening to
 365 recordings of their imaginal exposure, and completing in vivo exposures. Since mPE requires considerable time and
 366 effort, the study team will work with the participant to receive a release from work while participating in the treatment.

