450 devices are monitored by state-of-the-art monitoring applications that include configuration audit, management, and
451 availability 24x7.

458 The UTHSA STRONG STAR data server is currently a VMware Instance running Windows Server 2016 Enterprise
 459 Standard with daily backup services and vSphere Business Continuity Advanced Failover.

460
 461 Only select STRONG STAR Data and Statistics Services personnel have direct access to the data on a "need to access
 462 basis"; for example (but not limited to) detecting and repairing data corruption and producing reports not currently within
 463 the STRONG STAR system. STRONG STAR Data and Statistics Services also follows the Principles Of Least Privilege
 464 (POLP). All user activity is tracked and recorded within the system so if any records are added, altered, or viewed the
 465 action is recorded and can be recalled for auditing purposes. Access to this information will require a password-protected
 466 login available only to authorized STRONG STAR Data and Statistics Services staff.

467
 468 Every member of the Research Team will be trained and monitored about how to handle and protect both medical and
 469 research records. Furthermore, the Research Team strictly controls access to study data.

470
 471 The STRONG STAR Data Safety and Monitoring Plan (DSMP) that has been developed in accordance with the National
 472 Institutes of Health Office of Human Research Protection to assure the appropriate clinical safety monitoring of study
 473 subjects participating in research will be used to monitor this study.

474 475 7.4. Statistical Consideration

476 477 7.4.1. Sample Size Estimation.

Estimate Required Sample Size (Completed / Evaluable)	24
Estimate Participant Drop Out / Withdrawal after Randomization/Inclusion	4 (17%)
Total Required to Randomize / Include	28
Estimate Participant Screen Fail / Exclusion	12 (30%)
Total Required to Consent	40

478
 479 7.4.2. Primary (i.e., primary outcome variables) and secondary endpoints
 480 **Health Questionnaire and Self-Report Measures:** The primary aim of this pilot is to explore the potential feasibility,
 481 safety, and effect of CBD in reducing PTSD symptoms compared to placebo in retired service members receiving mPE.
 482 Therefore, the primary outcome variables will be the CAPS-5 total score, the PCL-5 total score, and adverse event

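### Blocks of four within four strata do not guarantee 12:12, and the planned 12 CBD and 12 placebo containers carry no overage for the imbalance that results

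*Combined protocol and SAP*

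**What the plan says.** Section 6 (Research Design) describes a permuted block "randomization design stratified by PTSD severity median score of 51 on the PCL-5 and population type (military or" civilian). Two binary factors give four strata. On the blocks it says: "Participant randomization will be subdivided into randomized blocks of four, two patients in each block will be" assigned to CBD and the other two to placebo. Its reason for blocking is: "Permuted block randomization is advantageous in small clinical trials to ensure equal allocation of participants in each" condition. The planned split is 12 and 12, as in the abstract: "enroll 24 individuals with PTSD to be randomized to CBD (n=12) or placebo (n=12) and all participants will receive 10" daily PE sessions.

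Section 7.3 (Interventions) has the pharmacy obtain enough "CBD for 12 participants from their supplying manufacturer. They will then prepare CBD (n = 12) and matching placebo (n" also 12), in blinded containers numbered according to the randomisation design. That is 24 containers. No overage, resupply step or rule for an exhausted arm is stated.

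Section 7.1 gives different totals: "Target number randomized: 28" and "Target enrollment number for completers: 24". The table in Section 7.4.1 agrees with Section 7.1. Its row "Estimate Participant Drop Out / Withdrawal after Randomization/Inclusion" shows 4 (17%), which leads to 28 randomised.

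**The concern.** Blocking guarantees equal arms only where every block is filled. A single list of 24 has that property. Four separate lists have it by design only if each stratum happens to stop at a multiple of four, and stratum sizes are not known in advance. Each unfinished block can leave its stratum out of balance by 1 or 2. Section 6 therefore claims a property that its own stratification removes.

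This matters mainly because the supply plan relies on that property. With exactly 12 containers per arm and 24 participants, any inequality means that a list calls for a 13th container of one arm. If none is available, staff must pause, order more, or hand out what is left. In the last case the closing allocations are set by stock and not by chance. The trial exists largely to show that its procedures are workable for a larger study, so a randomisation and supply process that can be followed to the end is part of what it tests.

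**Working it through.** **Inputs.** Four strata, blocks of four at 2:2, and 12 + 12 planned (Section 6); 12 + 12 containers (Section 7.3); 28 randomised for 24 completers (Sections 7.1 and 7.4.1). Stratum shares are not given, so they are an assumption and are varied below.

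**The plan's figure.** With one unstratified list, 24/4 = 6 full blocks and 6 × 2 = 12 per arm, so 12:12 is certain. The sample-size table is also consistent with itself: 24 + 4 = 28, 4/24 = 17%, 28 + 12 = 40 and 12/40 = 30%.

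**With strata.** If a stratum ends with r = (size mod 4) places filled in its open block, the chance that k of them are CBD is C(2,k)·C(2,r−k)/C(4,r). The imbalance (CBD minus placebo) is then:

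- r = 0: 0
- r = 1 or 3: +1 or −1, probability 1/2 each
- r = 2: +2 or −2, probability 1/6 each; 0 with probability 2/3

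Two cases can be checked by hand. With sizes 7/7/5/5, every stratum contributes ±1, and P(12:12) = C(4,2)/2⁴ = 6/16 = 37.5%. With sizes 6/6/6/6, P(12:12) = (2/3)⁴ + 12·(1/6)²·(2/3)² + 6·(1/6)⁴ = 0.198 + 0.148 + 0.005 = 35%.

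For the overall probability, stratum sizes are taken as multinomial and the imbalances are summed over strata, exactly. In the table, the first split is one population type against the other, and the second is the PCL-5 split.

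| Assumed mix, n = 24 | P(12:12) | P(unequal) |
|---|---|---|
| 50/50 × 50/50 | 0.433 | 0.567 |
| 70/30 × 50/50 | 0.431 | 0.569 |
| 80/20 × 50/50 | 0.425 | 0.575 |
| 80/20 × 80/20 | 0.445 | 0.555 |
| 90/10 × 80/20 | 0.462 | 0.538 |
| 95/5 × 90/10 | 0.497 | 0.503 |
| 98/2 × 50/50 | 0.558 | 0.442 |
| two strata only, 50/50 | 0.625 | 0.375 |
| two strata only, 80/20 | 0.627 | 0.373 |

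With equal strata the splits are 12:12 in 43.3%, 13:11 in 48.4%, 14:10 in 8.0% and 15:9 or worse in 0.3%. All four strata end on complete blocks in only 1.6%; the other 12:12 outcomes arise because imbalances cancel. At n = 28 with equal strata, P(equal) is 0.432.

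**Supply at 24.** P(a 13th container is called for) = 1 − P(12:12), so about 0.37 to 0.57 over these mixes. In simulation with equal strata, the first such call comes at participant 24 in 31% of trials, at 23 in 17%, and at 22 or earlier in 8%. These figures let any container serve any stratum. If containers were tied in advance to stratum lists, a shortfall would be more likely.

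**Supply at 28.** 28 − 24 = 4 containers short, whatever the blocking.

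**Overage.** With equal strata at 28, 15 per arm is exceeded with probability 0.084 and 16 per arm with probability 0.003.

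**Precision.** Variance of the group difference relative to 12:12: for 13:11, (1/13 + 1/11)/(2/12) = 1.007; for 14:10, (1/14 + 1/10)/(2/12) = 1.029.

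**The case against.** The strongest reply is that a run-out is inferred and not documented. A reader might conclude that the site will run out and be forced to give the last participants whatever remains. The documents do not say so. Section 7.3 states planned quantities and does not say that no more can be made. The pharmacy buys an approved product and compounds the placebo itself. One course is 5 mL × 18 days = 90 mL against a 100-mL bottle, so a 13th CBD course is one more bottle. Section 6 also has the code-holder coordinate with the pharmacy so that the blocking is carried out, which suggests following the list. This stands: forced allocation is a risk the plan leaves open, not one it commits to.

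Second, a reader might infer that unequal arms weaken the comparison. They do not to any useful degree: 13:11 costs 0.7% in variance and 14:10 costs 2.9%, in a pilot that states it is not powered for efficacy. Nor does the code-holder's advance knowledge add a harm, since that person sets all the codes and the containers are blinded to everyone else.

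Third, it is tempting to say that supply fails more often than not. That depends on the stratum mix. Sections 7.4.2 and 11 speak only of service members, while Sections 6 and 7.1.1 also admit civilians. If recruitment is almost all military, the figure falls below one half.

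Fourth, at the stated 28 randomised the containers run out anyway, so much of the supply problem belongs to the conflict between 24 and 28. This is largely right. But raising supply to 14 + 14 would leave the same defect, because arms of 28 are equal no more often than arms of 24.

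**Conclusion.** The point holds in a limited form. Equal allocation is not ensured under the stated stratification: 12:12 is reached in about 43% of trials of 24 with reasonably mixed strata, in about 50-56% if one population type makes up 95-98%, and in 63% if only two strata fill. The mix is an assumption, but none of the stratified cases tried brings the probability near 1.

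The consequence is procedural. In roughly 37-57% of trials of 24, the lists would ask for a container that the supply plan does not include. Unless the pharmacy prepares more, usually the last one or two allocations would then follow stock and not the list. The documents support neither a claim that this will happen nor a claim that precision suffers. What they do show is that the randomisation statement, the container count and the number randomised do not fit together, and that no rule covers an exhausted arm.

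**What to change.** In Section 6, replace the claim of ensured equality with a statement that allocation is balanced within completed blocks in each stratum, so that arm totals are approximately equal.

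In Section 7.3:

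- Reconcile the container count with the number randomised (24 in the abstract and Section 6, 28 in Sections 7.1 and 7.4.1).
- Replace the fixed 12 + 12 with four stratum-specific lists, and either have the pharmacy prepare each container on demand at randomisation or hold a modest overage per arm. At 28 randomised, 16 per arm would be exceeded with probability about 0.003, provided any container can serve any stratum.
- State that the list, never the remaining stock, determines each allocation.

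The cost is protocol wording, an instruction to the pharmacy, and drug and placebo for a few more assignments: 16 + 16 = 32 containers is four more than the 28 randomised. No extra participants are needed. A single unstratified list would restore exact 12:12 at 24, but would give up balance on severity and population type, so it is not the better choice merely to make the wording true.
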